Discharge	The patient is discharged and leaves the hospital alive. This does not include if a patient is moved to another unit.
	The time to discharge = the elapsed time (in days) from Day 1 to the earliest day at which the patient is Discharged from hospital (= Day where the 7-point ordinal scale score is equal to 1 or 2).
Improvement in	A decrease from baseline of at least one point in the 7-point ordinal score (eg, 5
clinical status	to 4).
Worsening	An increase from baseline of at least one point in the 7-point ordinal scale score
clinical status	(eg, 5 to 6).

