8.2 General Principles

This is a double-blind, placebo controlled randomized pilot study which may inform on treatment effect for future studies.

All analyses are considered exploratory and hypothesis-generating. All tests will be two-sided at 5% significance level. Hypothesis tested for the primary endpoint will be if addition of ensifentrine to SoC for up to 29 days could increase the proportion of patients with recovery versus standard of care plus placebo. The status according to the 7-point ordinal scale of all patients regardless of treatment withdrawal will be followed up during the scheduled treatment period (Day 29) and at a follow-up Day 60, or as far as possible.

Secondary endpoints are tested independently and there will be no adjustment for multiple tests.

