8.5 Missing Data

All attempts will be made to collect all data per protocol.

 The patients withdrawn from treatment will be followed up regarding their status according to the 7-point ordinal scale at Day 29 as far as possible (exceptions for patients with withdrawn consent or lost to follow-up) and this data will be the primary source for handling missing data in the study.

Any data point that appears to be erroneous or inexplicable based on clinical judgment will be investigated as a possible outlier.

• If data points are identified as outliers, sensitivity analyses may be performed to examine the impact of including or excluding the outliers. Any substantive differences in these analyses will be reported.

For survival analyses, patients with death as outcome will be censored at Day 29 (Day 60), unless the required event was reached prior to death. Patients who are lost to follow-up or terminate the study prior to Day 29 (Day 60) for other reason than death and prior to observing/experiencing the event will be censored at the time of their last observed assessment.

The only time to event analyses is the time to recovery.

For secondary endpoint analyses, the following imputation rules will be used for patients who are lost to follow-up, terminate early from the study, or do not have further outcome data available after discharge for any reason than death:

- Patients with no data collected at the actual time point of interest for other reason than
 death, the last assessment of their status prior to this time point will be used as a
 representative for that time point. Especially, if the patient's clinical status scale is 1 or 2
 at the last observed assessment, then the patient will be considered to be recovered
 through Day 29.
- For endpoints assessing total time (oxygen or non-invasive ventilator care), the status for patients with no data collected for other reason than death, will be assumed unchanged from last assessment of the score up to last day in the definition of the endpoint (Day 29). Thus, no extra days will be added for patients without oxygen or patients without non-invasive ventilator care at last assessment.
- Patients that die in the study will be handled as worst case in all the analyses, that is they are considered to be on oxygen need, non-invasive and invasive mechanical ventilator need for all time points following the death.

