- In analyses of oxygen need, patients in ventilator care (non-invasive or invasive mechanical) will be considered in oxygen need for the corresponding time period and patients with death as outcome will be considered in oxygen need for the remainder of the time period of evaluation.
- In analyses of non-invasive ventilator need, patients that require invasive mechanical ventilation will be considered also as having a non-invasive ventilator need. Patients with death as an outcome will be considered as having non-invasive ventilator need from

pg. 19 Confidential

time of death for the remainder of the time period of evaluation.

- In analyses of invasive mechanical ventilator need, patients with death as an outcome will be considered in invasive mechanical ventilator need for the remainder of the time period of evaluation
- The change from baseline in the 7-point ordinal scale will use the baseline score and the score at the endpoint using imputation for missing data as stated above, that is the last assessment of their status prior to this time point will be used.
- If the patient is discharged and no further hospitalization data are available, then the
 patient will be assumed to not have been readmitted. Thus, no additional imputed days
 on hospitalization will be added to the number of days recorded on available
 assessments for these patients.

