Day 1 - Day 29	n		
-	Yes		
	No		

pg. 54 Confidential

⁽or discharge, whichever was first)
*7-point ordinal scale score = 1, 2, 3, 4 or 5. n = number of patients with recorded value

Table 14.2.11: Summary of Proportion of patients re-hospitalized following initiation of study medication and subsequent discharge (over 60 days), ITT

Proportion of Patients	Re-hospitalized	Enrolled (N=45)	Ensifentrine (N=30)	Placebo (N=15)
Day 1 - Day 60	ay 1 - Day 60 n			
	Yes			
	No			

n = number of patients with recorded value

Table 14.2.12: Duration of hospitalization from initiation of study medication (Day 1 - Day 29 (or discharge, whichever was first); measured in days), ITT

Days of hospitalization	Enrolled		Placebo p-value*
from Day 1	(N=45	(N=30)	(N=15)
Median (Q1 - Q3)			

^{*}Wilcoxon rank sum test

Hospitalized = # days where the 7-point ordinal scale score = 3, 4, 5 or 6.

Discharge = The patient is discharged and leaves the hospital alive.

pg. 56 Confidential

Table 14.2.13: Change from Baseline in 7-point Ordinal Scale at Days 7, 14, and 29, ITT

Change from 7-point Ordin	n Baseline in nal Scale	Enrolled (N=45)	Ensifentrine (N=30)	Placebo (N=15)
Day 7	n Mean (SD)	()	()	()
Day 14	n Mean (SD)			
Day 29	n Mean (SD)			

Computed from Day 1 scale minus Day 7, Day 14, and Day 29 scale accordingly (or discharge) (or discharge, whichever was first)

pg. 57 Confidential

Table 14.2.14: Total time on Supplemental Oxygen (Day 1 - Day 29; measured in days), ITT

Days of Suppl	emental Oxygen	Enrolled	Ensifentrine	Placebo
(Scale=4)		(N=45)	(N=30)	(N=15)
Day 1 - 29	Median (Q1 - Q3)			

Hospitalized patient: 7-point ordinal scale score = 4, 5, or 6. Or 7-point ordinal scale score is equal to 7 if patient dies while hospitalized between Day 1-29.

Not hospitalized patient supplemental oxygen = # days where the 7-point ordinal scale score is equal to 2 (if required to have home oxygen).

pg. 58 Confidential

Table 14.2.15: Total time of non-invasive ventilation or high flow oxygen use (post-dose Day 1 - Day 29 (or discharge, whichever was first); measured in days)

Days of non-invasive ventilation or High Flow Oxygen Use (Scale=5)		Enrolled (N=45)	l Ensifentrine (N=30)	Placebo (N=15)
Day 1 - 29	Median (Q1 - Q3)			

Non-invasive ventilation or high flow oxygen use = # days where the 7-point ordinal scale score is equal to 5 or 6. Or 7-point ordinal scale score is equal to 7 if patient dies while hospitalized between Day 1-29.

pg. 59 Confidential

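### The footnote to SAP shell 14.2.13 uses the discharge score as the Day 29 score for anyone discharged earlier, against SAP 8.5, and reverses the sign of the change

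*SAP*

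**What the plan says.** The footnote to SAP shell 14.2.13 defines the tabulated change: "Computed from Day 1 scale minus Day 7, Day 14, and Day 29 scale accordingly (or discharge) (or discharge, whichever was first".

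The body of the SAP gives a different rule for the same endpoint. SAP 8.5 compares baseline with the "score at the endpoint using imputation for missing data as stated above, that is the last" available one before the time point. That fallback applies only under a condition, which opens "Patients with no data collected at the actual time point of interest for other reason than" and then names death. For deaths, 8.5 has its own rule, which begins "Patients that die in the study will be handled as worst case in all the analyses, that is" and goes on to count such patients as in need of oxygen and ventilation from then on. SAP 9.4 repeats the worst-case rule for the secondary endpoints. SAP Table 5 sets the change at Days 7, 14 and 29 with no stop at discharge. SAP 8.2 says that the ordinal status "of all patients regardless of treatment withdrawal will be followed up during the scheduled treatment period (Day 29") and again at Day 60.

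Protocol 8.5 supplies the data: a contact 4 to 10 days after discharge, one at 26 to 32 days after first dose, and one at Day 60, each recording the ordinal scale.

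On direction, SAP Table 4 defines improvement as "A decrease from baseline of at least one point in the 7-point ordinal score". SAP 9.4.3 plans an ANCOVA with treatment difference, confidence interval and p-value. Shell 14.2.13 has rows only for n and mean (SD).

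The discharge clause recurs with shell 14.2.10, in the titles of 14.2.16 to 14.2.18, and in the day-count shells 14.2.12 and 14.2.15, the last titled "Total time of non-invasive ventilation or high flow oxygen use (post-dose Day 1 - Day 29 (or discharge, whichever was first); measured in days".

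**The concern.** Shells are what a programmer works from. If the footnote is followed, the row labelled Day 29 does not hold Day 29 data for anyone discharged earlier. Protocol 4.3 cites a median stay of 10 to 13 days among survivors, so this would be a large share of patients. Someone sent home at score 2 and then readmitted or dead before Day 29 would still be tabulated as improved, although a later score or vital status has been collected.

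The sign is a separate matter. On this scale 1 is best and 7 is death, so a usual change from baseline is negative when a patient improves. The shell prints improvement as positive under a change-from-baseline title and gives no key. A reader could take +2 for deterioration.

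**Working it through.** The plan gives no power, effect size, SD or event rate for this endpoint, so there is no figure to reproduce. The check compares the two rules patient by patient.

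**Inputs**
- Arm sizes: 30 ensifentrine, 15 placebo (SAP Table 1).
- Scale: 1 to 7, death = 7 (Protocol Table 10).
- Baseline 4: the header of shell 14.1.5b shows 44 of 45 patients at 4.
- Assumed: discharge at score 2 (1 as the alternative), and the worst-case rule for death read as score 7.

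**Formulas**
- Shell: Day 1 score − discharge score.
- SAP 8.5: Day 29 score − baseline.
- Discrepancy with both on the SAP 8.5 sign: Day 29 score − discharge score.
- Shift in the arm mean: discrepancy ÷ arm size.

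Baseline 4, discharged at 2:

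| Day 29 state | Shell prints | Shell value, sign reversed | SAP 8.5 | Discrepancy | Placebo mean (÷15) | Ensifentrine mean (÷30) |
|---|---|---|---|---|---|---|
| Still out, score 2 | +2 | −2 | −2 | 0 | 0 | 0 |
| Readmitted on oxygen, 4 | +2 | −2 | 0 | 2 | 0.13 | 0.07 |
| Readmitted, invasive ventilation, 6 | +2 | −2 | +2 | 4 | 0.27 | 0.13 |
| Dead, 7 | +2 | −2 | +3 | 5 | 0.33 | 0.17 |

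The shell prints the same +2 on all four paths. With discharge at 1, a death gives 6/15 = 0.40 or 6/30 = 0.20, and a readmission at 4 gives 3/15 = 0.20 or 3/30 = 0.10. The clause also drops gains after discharge: a move from 2 to 1 is a discrepancy of 1 the other way, 1/15 = 0.07 or 1/30 = 0.03.

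**Proportion shells (14.2.10, 14.2.16 to 14.2.18).** One patient whose category changes after discharge is 1/15 = 6.7 or 1/30 = 3.3 percentage points. For 14.2.10 that means death or invasive ventilation/ECMO; readmission on oxygen alone does not change it.

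**Days 7 and 14.** Daily scoring stops at discharge (Protocol 8.1), and no post-discharge score is scheduled on either day. For most patients already discharged, SAP 8.5 would itself carry the last score forward and agree with the shell. The rules part when a death or readmission is known, or when the discharge contact records a changed score by then. The earliest contact is 4 days after discharge, so it can fall by Day 14 for someone discharged by Day 10.

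**Sign.** The shell variable, discharge clause aside, is −1 times the usual change. Least squares then negates the treatment coefficient and mirrors its interval. In an illustrative ANCOVA on 45 simulated patients (30 and 15), the estimate went from 0.274 (95% CI −0.863 to 1.410) to −0.274 (−1.410 to 0.863), with p = 0.630 both times.

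**The case against.** The strongest reply is that the footnote sits under example shells, which the SAP preface treats as samples, while the body already has the right rule. That stands in part. A reader might infer that events after discharge never reach the Day 7, 14 and 29 results. The documents support this only if the shell governs, and then mainly for Day 29. But the SAP states no precedence, so the conflict is real.

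A reader might also infer that relapse is hidden. It is not. The primary shell 14.2.3 has no discharge cut-off, 14.2.6 reports recovery through Day 60, 14.2.9 reports mortality at Days 29 and 60, and 14.2.11 reports re-hospitalization to Day 60.

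Nor do the documents show that the clause favours the arm with earlier discharge. That depends on which arm has events or gains after discharge, and no counts are given. Shell 14.2.9 carries 0 (0%) in its ensifentrine column at both times. That may be a placeholder, but if real, readmission is the relevant example in that arm.

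On the sign, Table 4 defines improvement and gives no formula for change, and the footnote states its subtraction openly. Table and model would point in opposite directions only if two differently signed variables were programmed, which nothing requires. This part of the objection holds.

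Finally, in 14.2.10 it is less clear which line the clause qualifies, so the reading there is less certain than for 14.2.13.

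**Conclusion.** The point holds as a conflict between shell and body. Read literally, the footnote to 14.2.13 contradicts SAP 8.5, the worst-case rule for deaths in 8.5 and 9.4, and Table 5, and it leaves the Day 29 contact score unused. Programming to the shell would give a wrong Day 29 result for any patient whose score changes between discharge and Day 29.

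The size is known only per event: 0.33 or 0.17 on the arm mean for a post-discharge death, 0.13 or 0.07 for a readmission at score 4, and 6.7 or 3.3 percentage points in the proportion shells (placebo and ensifentrine respectively). These figures rest on baseline 4, discharge at 2, death scored 7 and full arms of 15 and 30. The discharge-day score is itself uncertain, because Protocol 8.1.1 records the worse score of each day, which may still be a hospital category. In-hospital deaths are unaffected, since SAP Table 4 defines discharge as leaving alive.

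The reversed sign is a labelling fault only. The endpoint is secondary in an unpowered, exploratory pilot, but the correction is cheap and worth making.

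**What to change.** - **14.2.13:** replace the footnote with *score at Day 7, 14 or 29 minus baseline; negative = improvement; death = 7; missing data per SAP 8.5*. Add rows for the ANCOVA difference, 95% CI and p-value with the same sign.
- **14.2.13, 14.2.10 and 14.2.16 to 14.2.18:** delete the discharge clause, so that the Day 29 contact score is used and the last score is carried forward only under SAP 8.5.
- **14.2.7 and 14.2.8:** the clause also trails the definition of improvement here. State what it qualifies or remove it. The 14.2.8 footnote calls improvement an increase and should be corrected to match Table 5.
- **14.2.12:** align with SAP 9.4.6, which sums days over separate intervals. Count readmission days up to Day 29 from the recorded date and duration. The follow-up form (Protocol Table 15) covers only COVID-related readmission after at least 24 hours out of hospital, and the footnote should say so.
- **14.2.15:** align with SAP 9.4.5 as far as the data allow, and state that ventilation or high-flow days during a readmission are not collected. They cannot be rebuilt from the follow-up form.
- **14.2.5:** leave as it is, because discharge is recovery by definition.

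The cost is shell edits and some reprogramming, with no new data. Results may be slightly less favourable because events after discharge count, although gains after discharge will count too.
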